8.5.1 Follow-up of SAE

All SAEs will be followed until satisfactory resolution or until the principal investigator or sub-investigator deems the event to be chronic or the subject to be stable.

8.5.2 Serious AE Detection and Reporting

All SAEs will be:

- Recorded on the appropriate SAE report form.
- Followed through resolution by a study physician.

Timelines for submission of an SAE form are as follows:

- All deaths and life-threatening events regardless of relationship, will be recorded on the SAE form and the PI will be notified within 24 hours of identification of the SAE.

All SAEs determined to be related to study procedures will be reported to the Human Subjects Division of the University of Washington within 10-days of becoming aware of the event.

8.5.3 Reporting of Pregnancy

Pregnancies occurring in study subjects will be recorded.

8.6 Type and Duration of Follow-up of Subjects after Adverse Events

Adverse events will be followed until resolved or considered stable.

9 STATISTICAL CONSIDERATIONS

9.1 Outcomes

Aim 1. The primary outcome will be quantity of *L. crispatus* measured by qPCR at all available follow-up visits and will be compared during five months of CVR use to one month prior to CVR use. Secondary outcomes will be BV defined clinically by Amsel and confirmed by Nugent criteria at any follow-up visit, quantities of other BVAB defined by qPCR assay, and reported genital adverse events. Quantity and presence of other lactobacilli and BVAB species detected by PCR will be assessed using the methods outlined above. All available follow-up observations will be used. Quantity of *L. crispatus* will be log transformed and analyzed using a linear mixed model with subject random effect to account for correlation within person. Binary outcomes will be analyzed using generalized estimating equations with log link and robust standard errors to estimate relative risks while accounting for correlation.

Aim 2. The outcomes of interest will be compared within participants, using each woman as her own control; observations from the time prior to CVR initiation will be compared to those collected during CVR use. We will use methods for Normal data and then use non-parametric approaches or dichotomize and use binomial link GEE if data are highly skewed and cannot be transformed into a Normal distribution. Some analyses will be exploratory; we will compare quantities of several immune mediators noted above by CVR use. These comparisons will not likely be independent, so we will adjust for multiple comparisons by permutation procedure. We will also correlate concentrations of immune mediators with qPCR results in Aim 1 to test the hypothesis that higher concentrations of protective lactobacilli will be associated with higher levels of protective mediators, and lower levels of inflammatory cytokines/chemokines. Continuous variables between comparison groups will be compared using t-tests or Wilcoxon rank-sum tests, and dichotomous variables will be compared by chi-square tests or Fisher's exact tests. Linear mixed effects models or generalized estimating equation (GEE) models will be used to examine whether outcomes (mediator concentrations, vaginal bacterial

quantities) differ significantly between comparison groups after adjustment for confounding factors identified through univariate analysis. All analyses will assume a two-sided significance level of 0.05.

Aim 3. The primary outcomes will be (1) incidence of BV at all available follow-up visits, and (2) time to BV during four months of CVR use relative to the two months prior to CVR use. For secondary analysis, we will measure the quantity of HSV-2 by PCR. This will be log transformed and association with CVR use examined using a linear mixed model as for Aim 1. *Sample size calculation:* Data from our prospective studies of BV were used to estimate the likelihood of these conditions occurring during follow-up. Over six months of observation, we have documented BV recurrence rates after cure of an initial BV episode of 28 / 100 person-years in absence of any hormonal contraception. A recent meta-analysis estimated that HC was associated with a 30% reduced likelihood of BV.²⁵ With these assumptions, we will have reasonable power to detect a 30% or greater difference in incidence of BV by CVR status (Table 5). However, BV incidence may be lower, and mechanisms for a favorable shift in vaginal microbiome, if affected by CVR, may be heterogeneous. If so, we will still be able to generate important preliminary data in support of the CVR's favorable effect on the vaginal environment through demonstration of improved microbiome maintenance and immune profile; this would support future study of the CVR in populations with higher incidence of BV and other cervicovaginal STI.

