5.4 CVR Use

After one month (Month 2 visit), women will be asked to initiate NuvaRing use using one of the

following two approaches. Participants will choose the approach they prefer, and will be provided standard counseling and health information about the risks and benefits associated with each:

- Continuous CVR use for four 28-day cycles, with replacement of the CVR after each cycle
- Non-continuous CVR use involving use for 21 days, then removal for 7 days, with replacement after the 7-day CVR-free period

Participants will initiate CVR use at any time in the cycle, with backup contraception (condoms) to cover the appropriate time period. We will follow standard guidelines from the U.S. Centers for Disease Control and Prevention (CDC), the Selected Practice Recommendations for Contraceptive Use, which state that women who initiate CVR within 5 days of the start of menstrual bleeding do not require backup contraception. Women initiating CVR >5 days after the start of menstrual bleeding require backup protection for the next 7 days.

While the package insert mentions initiation early in cycle, we aim to keep the number of pre-initiation visits to a minimum. After four months of CVR use (at Month 6 visit), women will be offered the option to discontinue use of the CVR, will be provided condoms and will then be assessed again after one month. Women may elect to continue CVR use at the Month 6 visit. CVR will be provided by the study.

For subjects who opt for continuous CVR use and prefer to have their CVR removed by the study clinician, the CVR will be saved for future analysis.

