6.3.2 Hormonal Sub-Study Visit 1b (Cycle day 6-10 or Cycle day 20-25)

For women enrolled in the hormonal sub-study, additional samples will be collected at two specific time points during their menstrual cycle prior to CVR initiation: follicular phase (cycle day 6-10) and luteal phase (cycle day 20-25).

- The first visit will be timed to occur at Enrollment or Month 1, depending on cycle day.
- The second (and additional) visit (Visit 1b) will occur outside their monthly study visits, timed to capture their other cycle phase; either before or after Month 1 depending on cycle timing. Procedures at Visit 1b will be identical to the monthly visits.

Additional Sub-Study Samples: At each sub-study visit, a cervical cytobrush specimen will be collected during the pelvic exam and blood will be drawn (1.0 mL) to measure progesterone levels.

6.3.3 Month 2

A pelvic exam will be performed and study specimens will be collected. Information on symptoms, sexual behavior, antibiotic and hormone use, condoms and douching will be collected via interview and questionnaire. In addition, CVR will be initiated at this visit. Daily home swab samples from the previous 30 days will be collected and reviewed. Subjects will be provided with a new daily home collection kit and instructions for collecting specimens over the next 30 days following CVR use.

6.3.4 Months 3, 4 and 5

A pelvic exam will be performed and study specimens will be collected. Information on symptoms, sexual behavior, antibiotic and hormone use, condoms and douching will be collected via interview and questionnaire at each visit. New CVRs will be dispensed. At the Month 3 visit, daily home swab samples from the previous 30 days will be collected and reviewed.

For women enrolled in the *optional hormonal sub-study*, at the Month 3 visit, a cervical cytobrush specimen will be collected during the pelvic exam and blood will be drawn (1.0 mL) to measure progesterone levels.

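### The Aim 1 primary model names one subject random effect and no robust standard errors, so its test is too liberal if the ring's effect differs between women

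*Combined protocol and SAP*

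**What the plan says.** Section 9.1, Aim 1, makes the quantity of L. crispatus by qPCR the primary outcome, "compared during five months of CVR use to one month prior to CVR use". It adds that "All available follow-up observations will be used". The log quantity is analysed with a "linear mixed model with subject random effect to account for correlation within person". No random effect of the ring, residual covariance structure or robust variance estimator is named for this model.

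The next sentence gives binary outcomes "generalized estimating equations with log link and robust standard errors to estimate relative risks". Section 9.1 also sets the error rate: "All analyses will assume a two-sided significance level of 0.05". Aim 3 reuses the Aim 1 linear mixed model for HSV-2 quantity.

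Sections 4.1, 5.4 and 6.2 bear on whether women will respond alike. Women choose continuous or 21/7 ring use themselves. They may enter with current BV or with only a recent history of it, and those still BV-positive at the 7-10 day visit may enrol. In section 9.1, Aim 3, the plan remarks that "mechanisms for a favorable shift in vaginal microbiome, if affected by CVR, may be heterogeneous".

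**The concern.** There is no control arm, so the Aim 1 conclusion rests on one within-woman contrast of on-ring with pre-ring values. A random intercept removes differences in level between women. It also assumes that every woman shifts by the same amount on the ring. If the shifts differ, all of a woman's on-ring rows share her personal deviation, but the model counts them as separate evidence about the mean effect.

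The confidence interval for the primary result would then be too narrow and its p-value too small. A mean gain in L. crispatus could be declared when gains in some women are offset by losses in others. The plan guards its binary outcomes against a misspecified correlation structure but does not do so for its primary continuous outcome.

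**Working it through.** **Inputs from the plan.**
- Section 9.2: 120 women enrolled and at least 75% with a pre-ring and a post-ring visit. 120 x 0.75 = 90 analysable women, which reproduces the plan's figure. Section 9.2 gives no effect size, SD or power for L. crispatus.
- Section 9.1: two-sided 5% level, all available observations.
- Section 6.3.3 (Month 2): "CVR will be initiated at this visit". Specimens from that visit are taken as pre-ring (an assumption).
- On-ring rows: four (Months 3-6), or five if Month 7 counts for women who continue. Section 9.1, Aim 1, speaks of five months of use, while sections 5.1 and 5.4 and Aim 3 speak of four. Pre-ring rows: one or two.

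**Assumed, because the documents do not give them.** σ is the visit-to-visit SD within a woman on the log scale, and τ is the between-woman SD of the ring effect. Only the ratio τ/σ matters.

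**Formulas.** Take a pre-ring and b on-ring rows per woman, balanced. The estimate is the average over women of (on-ring mean minus pre-ring mean).
- True variance per woman: τ² + σ²(1/a + 1/b)
- Variance reported by the random-intercept model: τ²/(a+b-1) + σ²(1/a + 1/b)
- Type I error: 2[1 - Φ(1.96 x √(reported/true))]

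The reported value is too small whenever τ > 0 and a+b > 2.

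**Worked case** (a = 2, b = 5, τ = σ = 1). 1/2 + 1/5 = 0.7. Reported: 1/6 + 0.7 = 0.867. True: 1 + 0.7 = 1.7. The SE ratio is √(0.867/1.7) = 0.714, so type I error is 2[1 - Φ(1.40)] = 16.2%. With 90 women the SEs are √(0.867/90) = 0.098 reported and √(1.7/90) = 0.137 true.

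**Type I error of the random-intercept test, closed form:**

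| Rows pre/on | τ/σ = 0 | 0.25 | 0.5 | 1.0 | 1.5 |
|---|---|---|---|---|---|
| 1/4 | 5.0% | 5.4% | 6.7% | 11.0% | 15.8% |
| 1/5 | 5.0% | 5.5% | 6.9% | 11.8% | 17.5% |
| 2/4 | 5.0% | 5.8% | 8.0% | 14.9% | 21.5% |
| 2/5 | 5.0% | 5.9% | 8.3% | 16.2% | 23.7% |

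If the Enrollment specimen is also a pre-ring row (3/4), the values at 0.25 to 1.5 are 6.0%, 9.0%, 17.7% and 25.4%. With exactly one row before and one after there is no inflation.

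**Simulation checks (90 women).**
- REML random-intercept fits with 15% of visits missing, 2,000 runs each. At τ/σ = 0.5: 5.0% (1/4), 6.6% (2/4), 7.8% (2/5). At 1.0: 11.8%, 13.6%, 15.8%. At zero: 3.8-6.2%, scattered around 5%.
- Woman-level cluster-robust SEs, 4,000 runs each, τ/σ from 0 to 1.5: 4.7-6.0% (2/5) and 5.1-5.4% (1/4). With 15% of visits missing: 5.1-5.9%.
- A test on per-woman differences, which in the balanced case equals a random ring effect: 4.2-5.6%. A random-slope model on incomplete data was not fitted.

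**Daily swabs.** HSV-2 quantity comes from daily swabs, so it has many more rows. With 30 rows before and 30 after, treated as independent given the woman, and σ as the day-to-day SD, the closed form gives 15.6%, 35% and 58% at ratios of 0.25, 0.5 and 1.0.

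**The case against.** - **The wording does not exclude a random ring effect.** True: the text is under-specified. But a lone subject effect is ordinarily read as an intercept, and nothing elsewhere adds a slope or robust SEs to Aim 1. If a slope is intended, stating it costs nothing.
- **A reader might infer that the protocol expects women to respond differently.** It does not go that far. The remark quoted from Aim 3 is conditional, concerns mechanisms, and is a caveat about power for BV incidence. Self-chosen regimens and mixed BV status make differing effects plausible but give no size.
- **A reader might take 16-24% as the trial's false-positive rate.** The documents do not support that. Those figures need effects that vary by 1 to 1.5 times visit noise and the fullest layout with complete data. If 5-10% of women gained 4 log10 and an equal share lost as much, the error would be 14-27% (σ = 1). That is the same assumption in another form, since it implies τ of about 1.3 to 1.8. With rows varying from 1-2 before and 1-5 after (also an assumption), the error is about 7% at a ratio of 0.5 and 11% at 1.0.
- **If the ring affects no woman, the test keeps its 5% level in this model.** Correct. The excess concerns a zero mean effect with non-zero individual effects. That null still matters, because the analysis estimates a mean change, and the interval is too narrow whenever effects vary.
- **Aim 2 allows GEE for bacterial quantities, and non-parametric and permutation methods.** Those provisions belong to Aim 2 and do not govern the Aim 1 primary model.

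**Conclusion.** The concern holds conditionally. On its ordinary reading, the primary model understates the standard error of the ring contrast if the effect on log L. crispatus differs between women. The direction follows from algebra, but the size cannot be fixed from the documents. With monthly visits only (1 pre/4 on to 2 pre/5 on), type I error is about 5.4-6% at a ratio of 0.25, 7-8% at 0.5, 11-16% at 1.0 and 16-24% at 1.5, with none of this excess at zero.

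This rests on the random-intercept reading, on visit errors that are independent given the woman, and on an assumed τ/σ. Because the excess is small at modest ratios and absent at zero, the point should be fixed, but it does not by itself invalidate the primary analysis.

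**What to change.** In section 9.1, Aim 1, replace the model sentence with: *linear mixed model with a subject random intercept and woman-level cluster-robust standard errors (or with a random CVR effect per woman)*. Choose one before the data are analysed. Apply the same wording to the other log-quantity outcomes that use this model, including HSV-2 quantity in Aim 3.

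In the same edit, state which visits are pre-ring and on-ring rows, reconcile five with four months of ring use, and say whether daily swabs enter the primary model. Each of these changes the number of rows per woman, and so the size of the problem.

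The cost is one or two sentences and no new data. If effects are homogeneous, intervals are essentially unchanged. If they differ, intervals widen by the reciprocal of the SE ratio: 2-4% at a ratio of 0.25 (1/0.982 to 1/0.965), 7-13% at 0.5 (1/0.935 to 1/0.884) and 23-40% at 1.0 (1/0.816 to 1/0.714). That widening is precision the data do not contain.

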infections, and acquisition of multiple STI, including HSV2 and HIV.¹⁴ BV may elevate these risks in several ways, including activation of local immune cells. Finally, recent data indicate that onset of menstruation triggers key shifts in local vaginal bacteria, and in many women, may actually precipitate BV. Continuous use of the NuvaRing (use for four weeks, then replace) suppresses menstruation, and is increasingly used by many women with excellent reports of acceptability and safety. Whether this suppression of menstruation could suppress BV recurrence is not known.

Although short-term antibiotic therapy improves symptoms and restores *Lactobacillus* predominance in most women with BV, up to 20% of women fail routine therapy. In addition, BV recurrence after successful therapy is the rule. Recurrence is likely caused by failure to recolonize the vagina with desirable lactobacilli, which requires adequate vaginal estrogenization. In one study, women who used the NuvaRing for 3 consecutive 28-day cycles had higher quantities of desirable vaginal lactobacilli relative to women who used oral contraceptive pills containing 20 µg ethinyl estradiol and 100 µg levonorgestrel.¹ The NuvaRing releases 120 mcg/day of ENG (the active metabolite of desogestrel, a progesterone) and 15 mcg/day of ethinyl estradiol (the estrogen component). While generally well tolerated, incidence of local complaints (increased vaginal discharge or discomfort) with continuous CVR use is higher than those reported by OC users;¹⁵ thus, the risk: benefit ratio of this approach needs careful assessment.

Pregnancy is also an independent risk for HIV acquisition and transmission, when acquisition confers high rates of perinatal transmission.^{16,17} However, systemic depot progesterone, commonly used worldwide, may independently increase risk of HIV acquisition and transmission.⁸ Increased HIV risk related to hormonal contraceptive use would be of global public health importance, given the large number of women using such methods. In a recent technical report, the World Health Organization noted that “expansion of contraceptive method mix and further research on the relationship between hormonal contraception and HIV infection is essential.”¹⁸

For all of these reasons, then, a careful study of the microbiological, clinical, and immunologic benefits of the CVR is a high scientific and public health priority.

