1.2 Study Hypothesis

- CVR use will be associated with favorable vaginal changes assessed by BVAB qPCR, and community definition by high-throughput sequencing
- Initiation of CVR use will be associated with an increase in desirable protective factors in the vagina, including increases in SLPI and reduction in proinflammatory cytokines.
- CVR use will be associated with lower rates of and longer time to incident BV assessed by clinical status (Amsel criteria and symptoms)¹⁹ and Nugent score,²⁰ and among HSV-2-infected women, with a reduction in HSV-2 shedding.

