6.3 Follow up visits

Women will be asked to return for up to follow up visits monthly at Months 1, 1b (for those women participating in the Hormonal Sub-Study), 2, 3, 4, 5, 6, and end of study visit at Month 7 for repeat interview/questionnaire, pelvic examination, and collection of study specimens. Between all study visits, women will be asked to avoid self-treatment with over-the-counter vaginal medications until evaluated by study clinicians if possible.

At each follow-up visit, information on symptoms (vaginal discharge, pruritus), types, frequency, and timing of sexual behavior (oral, vaginal, anal), menstrual history, antibiotic and hormone use, lubricants, condoms, and douching will be collected. Additionally, pH and Gram stain of vaginal fluid, vaginal swabs for BVAB-specific PCRs and cervical fluid will be performed.

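### Aim 2 picks adjustment covariates by univariate screening, which can admit variables the ring itself changes; if one enters, the CVR coefficient no longer estimates the effect of starting the ring

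*Combined protocol and SAP*

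**What the plan says.** The hypothesis for the immune outcomes is in Section 1.2: "Initiation of CVR use will be associated with an increase in desirable protective factors in the vagina", together with a fall in proinflammatory cytokines. It concerns the effect of starting the ring and does not exclude any pathway.

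Section 9.1, Aim 2 sets the contrast within women: "observations from the time prior to CVR initiation will be compared to those collected during CVR use". Mediator comparisons by CVR use are to be adjusted for multiplicity by permutation. The paragraph then turns to comparison groups, which it does not define. First come simple tests: "Continuous variables between comparison groups will be compared using t-tests or Wilcoxon rank-sum tests". Then come models: "Linear mixed effects models or generalized estimating equation (GEE) models will be used to examine whether outcomes" (mediator concentrations and vaginal bacterial quantities) "differ significantly between comparison groups after adjustment for confounding factors identified through univariate analysis". The paragraph ends: "All analyses will assume a two-sided significance level of 0.05".

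There is no covariate list, no selection threshold, no exclusion of variables measured after ring start, and no statement of which test decides Aim 2. Section 2 lists local immune parameters among the primary outcomes.

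**The concern.** When the same women supply both periods, a factor that is fixed over time cannot be associated with period. A screen for confounders of the before/during contrast can therefore find only variables that changed between the periods.

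Section 6.3 re-measures many such variables at each follow-up visit: symptoms including discharge, sexual behaviour, pH, Gram stain, and "menstrual history, antibiotic and hormone use, lubricants, condoms, and douching will be collected". On the protocol's own account the ring changes, or is expected to change, several of them:

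- **Menses.** Section 1.1 says: "Continuous use of the NuvaRing (use for four weeks, then replace) suppresses menstruation".
- **Discharge.** Section 1.1 reports more local complaints with continuous ring use than with oral contraceptives.
- **Flora, pH and BV.** Sections 1.1 and 1.2 expect more lactobacilli, which keep pH low, and less BV. Section 9.1 also hypothesises that lactobacilli go with higher protective mediators.

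A variable on such a pathway is associated with both period and outcome because the study's hypothesis is true, so it would pass a univariate screen for that very reason. At stake is whether the adjusted model answers the Section 1.2 question. It could remove a real immune effect that works through the proposed mechanism, or show an effect when the total effect is zero.

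**Working it through.** **The plan's own figure.** Section 9.2 gives 120 women and at least 75% with a visit in each period: 120 × 0.75 = 90 analyzable women. This reproduces. No effect size, SD or power is given for Aim 2, so everything below is illustration.

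**Assumptions.** 90 women; 2 pre-ring and 4 on-ring visits (the schedule could supply a third pre-ring visit); within-woman residual SD 1; two-sided 0.05 (Section 9.1). Let R = 1 on the ring and 0 before, M a candidate covariate, and Y the outcome:

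- M = a·R + woman + e1
- Y = c·R + b·M + woman + e2, with corr(e1, e2) = ρ
- total ring effect = c + a·b

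**Formulas.**

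- Within-woman sum of squares of R: 90 × 6 × (2/6) × (4/6) = 120.
- Unadjusted test (ρ = 0 or b = 0): estimate c + a·b, SE = √((1 + b²)/120).
- Test adjusted for M: substituting e2 = ρ·e1 + independent error gives an expected CVR coefficient of c − ρ·a. SE = √((1 − ρ²)/(120·f)), with f = 450/(450 + 120a²) and 450 = 90 × 5.
- Rejection rate ≈ Φ(|z| − 1.96) + Φ(−|z| − 1.96).

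**Total effect 0.30, ρ = 0.**

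| Share through M | a, b, c | Unadjusted z and power | Adjusted z and power |
|---|---|---|---|
| one third | 0.5, 0.2, 0.20 | 0.30/0.0931 = 3.22; 90% | 0.20/0.0943 = 2.12; 56% |
| half | 0.5, 0.3, 0.15 | 0.30/0.0953 = 3.15; 88% | 0.15/0.0943 = 1.59; 36% |
| all | 0.6, 0.5, 0 | 0.30/0.1021 = 2.94; 84% | 0; 5% |

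**Total effect zero (b = c = 0), with M and Y sharing an unmeasured visit-level cause.** The unadjusted test rejects 5%.

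| a, ρ | Adjusted coefficient / SE | Rejection |
|---|---|---|
| 0.3, 0.3 | −0.09/0.0881 = −1.02 | 18% |
| 0.5, 0.2 | −0.10/0.0924 = −1.08 | 19% |
| 0.5, 0.4 | −0.20/0.0864 = −2.31 | 64% |
| 0, 0.4 (ring does not move M) | 0 | 5% |

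The tables take M as already selected. Simulation with an actual p < 0.05 univariate screen gives nearly the same answers: 57%, 36% and 5% in the first table; 18%, 19% and 64% in the first three rows of the second. In the first table's cases M was selected in at least 99.7% of runs. Selection depends on the screen and the size of the shift. With a smaller shift (a = 0.25), a total effect of 0.25 that is half mediated, and a screen requiring association with both period and outcome, M entered in about 79% of runs and rejection fell from 71% to 31%.

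**The opposite case.** Suppose a covariate differs between periods by −0.5 for a reason unrelated to the ring, its slope on Y is 0.5, and the ring does nothing. The unadjusted estimate is −0.25, z = −0.25/0.1021 = −2.45, and the test falsely rejects 69% of the time; the adjusted test rejects 5%. Here adjustment is right. The associations among R, covariate and Y have the same structure as in the fully mediated row, so no univariate screen can tell the two apart.

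**The case against.** The strongest reply is that the plan says it adjusts for confounding factors, and a consequence of the ring is not a confounder. A reader might infer from the screening rule that the adjusted model does condition on ring-changed variables and so tests a different null hypothesis. The documents do not support that, for four reasons:

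- No covariate is named. Bacterial quantities appear in the model sentence as outcomes, and their link with mediators has its own correlation analysis. Hormone use on the ring is the exposure itself and an implausible covariate.
- The term *comparison groups* is undefined and sits beside independent-group tests. It might cover continuous versus intermittent use, which women choose themselves (Section 5.4). Time-fixed confounding is real there and adjustment is needed.
- The paragraph also plans a within-woman comparison with no covariates mentioned, which does address Section 1.2. Nothing makes the adjusted model decisive.
- Every effect size above is assumed.

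A reader might also infer that adjustment should be dropped altogether. That does not follow either. Women with BV at enrollment receive antibiotics before the ring starts (Section 5.1), a documented factor that differs between periods for a reason other than the ring.

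What survives is narrower. The only stated way of identifying a confounder is univariate association, which cannot do that job in a before/during contrast, and no other text keeps ring-changed variables out.

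**Conclusion.** The concern holds as a risk left open by a stated rule, provided that the model compares before with during CVR. If a ring-changed variable enters, the CVR coefficient is at best the part of the effect not passing through it, and not even that when covariate and outcome share unmeasured causes. That direction follows from the design. The sizes, a loss from 84–90% power to between 56% and 5%, or false rejection of 18–64%, rest on assumed effects, two pre-ring visits and one selected covariate. If the ring does not move the covariate, no harm results. This is a cheap improvement, not a flaw that invalidates Aim 2.

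**What to change.** In Section 9.1, Aim 2:

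1. Define the comparison groups for each test and model.
2. Name the within-woman before/during contrast, without covariates the ring can change, as the main Aim 2 test for mediator concentrations and bacterial quantities.
3. Delete the clause on identification by univariate analysis. Fix any adjustment set in advance on causal grounds, limited to time-varying factors not affected by starting the ring, and include antibiotic treatment of BV given before ring start. Baseline factors may be added for any continuous-versus-intermittent comparison.
4. Report models with any of the following only as labelled exploratory mechanism or sensitivity analyses: menstrual bleeding; discharge or symptoms; pH; BV or Nugent status; bacterial quantities (for immune outcomes); BV or its treatment during ring use; condom use; STI. Condoms and STI belong here because condoms are supplied as contraception before the ring (Section 5.3) and the protocol expects the ring's flora to protect against STI (Section 1.1).

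The cost is wording in one section, with no new data, visits or participants. The downside is slightly more residual variance in the main test and one extra labelled exploratory model.
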